6.9.3. Body Weight

Weight will be measured at multiple visits in both treatment periods before dosing. Descriptive summaries of body weight will be provided for actual values of Day 1, Day 29, Day 57, Day 78 by treatment for each period, and by treatment only, and change from Day 1 values by treatment for each period, and by treatment only. Plots of mean body weight and mean changes from Day 1 over time will be provided by treatment for each period, and by treatment only.

6.10. Safety Analyses

Safety measures include, but not limited to, AEs, treatment-emergent adverse events (TEAEs), serious adverse events (SAEs), adverse events of special interest (AESIs), vital signs, and safety laboratory measures.

Unless specified otherwise, safety analyses will be performed on the safety population.

Unless specified otherwise, safety listings will display values/events during all study periods (i.e., treatment periods, washout, and follow-up period). Listings of AEs, death, SAE may include (but not limited to): patient identification (ID) number, age, sex, race, treatment, dose, Medical Dictionary for Regulatory Activities (MedDRA) System Organ Class (SOC), Preferred Term (PT), and time of onset from the first dose of study drug, duration of the AE, seriousness, severity, relatedness to study drug, action taken, and outcome, as appropriate. Additional safety listings will be provided for safety parameters other than AEs in related sections below. Treatment, and treatment period will be displayed in listings.

For safety measurements, summary statistics will be provided by treatment. A summary will be provided for AEs with frequency ≥ 10 patients with such event.

6.10.1. Adverse Events

A listing of adverse events for the safety population will be provided, which includes MedDRA SOC, and PT.

6.10.2. Treatment-Emergent Adverse Events

A TEAE is defined as an AE which first occurs post first dose of study drug (of Period 1) or which is present prior to first dose of study drug (of Period 1) and becomes more severe post first dose. The maximum severity for each AE during the baseline period (prior to first dose of Period 1) including ongoing medical history will be used as baseline severity.

Treatment-emergent adverse events will be summarized by treatment, severity and relationship with study drug.

For TEAEs in wash-out period, the treatment arm from Period 1 will be used for summary. For TEAEs in follow-up period, the treatment arm from Period 2 will be used.

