Abbreviations: AEs = adverse events; BP = blood pressure; CRU = clinical research unit; ECG = electrocardiogram; P = predose; PK = pharmacokinetics; PR = pulse rate; SMPG = self-monitoring of plasma glucose.

Note: If multiple procedures take place at the same time point, the following order may be consulted for prioritization: ECG, vital signs, glucose sampling, counter-regulatory hormone samples, safety laboratory tests, PK samples, immunogenicity samples, cognitive assessments, storage samples.

Study Schedule Protocol I8F-MC-GPHG: Washout Period

Procedure	Washout Period
Visit	
Study Week ^a	12-20 (12-22)
Study Day ^a	81-135 (81-149)
Clinical Procedures	
Washout / crossover	X
Concomitant medications	X ^b
AEs	X ^b
Glucose Management	
SMPG	X ^b

Abbreviations: AEs = adverse events; SMPG = self-monitoring of plasma glucose.

a Washout period is at least 8 weeks and up to 10 weeks, if necessary.

b Data will be reviewed and recorded in the electronic case report form at the dose 1 Period 2 visit.

Study Schedule Protocol I8F-MC-GPHG: Follow-up / Early Termination

Procedure	ET	Final FU	Comments
Visit	-	17	
Study Week	-	36	
Study Day	As soon as possible after discontinuation decision	Within 4 weeks from last dose/ET	
Clinical Procedures			
Weight	X	X	
Vital signs (BP/PR/body temperature)	X	X	Refer to screening table.
ECGs	X	X	Refer to screening table.
Concomitant medications	X	X	
AEs	X	X	
Physical examination / medical assessments	X	X	Refer to screening table.
Outpatient visit	X	X	
Glucose Management			
Review of study diary for SMPGa	X	X	
Study diary collection		X	
Laboratory Tests			
Pregnancy test (women of childbearing potential)	X	X	Refer to screening table.
Diagnostics			
PK sample	X	X	Samples for immunogenicity and PK to be time-matched as far as possible.
Immunogenicity	X	X	

Abbreviations: AEs = adverse events; BP = blood pressure; ECG = electrocardiogram; ET = early termination; FU = follow-up; PK = pharmacokinetics; PR = pulse rate; SMPG = self-monitoring of plasma glucose;

a SMPG will continue until Follow-up visit.

Note: If multiple procedures take place at the same time point, the following order may be consulted for prioritization: ECG, vital signs, PK samples, immunogenicity samples.

3. Introduction

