5.1.3. Washout Between Treatment Periods

There will be a washout period of at least 8 weeks, but not longer than 10 weeks, between the final dose of study drug in the first treatment period (on Week 12) and the first dose of study drug in the second treatment period based on tirzepatide's elimination half-life of approximately 5 days.

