10.3.1. Safety Analyses

10.3.1.1. Clinical Evaluation of Safety

The incidence of AEs for each treatment will be presented by severity and by association with IP, as perceived by the investigator. Adverse events reported to occur prior to study entry will be distinguished from those reported as new or increased in severity during the study. Each AE will be classified by the most suitable term from the medical regulatory dictionary.

All AEs and SAEs will be reported.

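### By-treatment TEAE tables have no cut-off after the last dose, so 56 to 70 washout days count toward the Period 1 treatment and at most 28 follow-up days toward the Period 2 treatment: a minor dilution, not a bias between treatments

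*SAP*

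**What the plan says.** SAP 6.10.2 defines a TEAE against the first dose of Period 1 only, and then assigns off-treatment events by period: "For TEAEs in wash-out period, the treatment arm from Period 1 will be used for summary" and "For TEAEs in follow-up period, the treatment arm from Period 2 will be used". The tabulation is by treatment: "Treatment-emergent adverse events will be summarized by treatment, severity and relationship with study drug". Protocol 10.3.1.1 names the measure: "The incidence of AEs for each treatment will be presented by severity and by association with IP". Neither document sets a cut-off after the last dose, a by-period TEAE table or an exposure-adjusted TEAE rate.

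The two off-treatment tails differ in length. Protocol 5.1.3 says of the first: "There will be a washout period of at least 8 weeks, but not longer than 10 weeks", running from the last Period 1 dose to the first Period 2 dose. The washout table in the Schedule of Activities agrees ("Washout period is at least 8 weeks and up to 10 weeks, if necessary") and says of adverse events in that interval: "Data will be reviewed and recorded in the electronic case report form at the dose 1 Period 2 visit". The final follow-up visit is due "Within 4 weeks from last dose/ET".

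**The concern.** Adverse events are a secondary endpoint, and the percentage of patients with an event depends on how long they are observed. Under the SAP rule the window attached to a treatment is longer when that treatment comes first, and part of the extra time falls when little drug remains.

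Other parts of the plan draw the boundary more tightly:

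- The abbreviations list in Protocol Appendix 1 ties a TEAE to a defined treatment period.
- SAP 6.6.1 ends exposure 7 days after the last dose.
- Protocol 5.1 and 5.1.3 justify the washout by a half-life of about 5 days, that is, as time for the drug to clear.

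SAP Section 8 does not list the wider TEAE window as a change from the protocol. At stake are some dilution of the tirzepatide-placebo contrast in TEAE incidence and, if dropout differs by treatment, somewhat unequal observation time.

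**Working it through.** **Inputs from the documents.** First dose Day 1 and last dose Day 78 of each period; washout 56-70 days; follow-up at most 28 days; half-life about 5 days; 1:1 sequences; 38 enrolled and 30 completing, so 8 expected dropouts.

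**The plan's own figures.** Screening and lead-in of 2 or 6 weeks + 12 + 8 + 12 + 4 = 38 or 42 weeks, which matches the stated study duration. The final follow-up falls at 12 + 8 + 12 + 4 = week 36, which matches the schedule.

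**Windows for completers.** From first to last dose is 78 − 1 = 77 days.

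- Period 1: 77 + 56 = 133 days (19 weeks) to 77 + 70 = 147 days (21 weeks).
- Period 2: 77 + 28 = 105 days (15 weeks) at most.
- Mean per treatment under 1:1 sequences: (133 + 105)/2 = 119 days, or (147 + 105)/2 = 126 days, the same for tirzepatide and placebo.
- Share of the pooled window more than 28 days after the last dose: 28/(133 + 105) = 12%, or 42/(147 + 105) = 17%, again the same for both.
- Drug left at 28 days: 2^(−28/5) = 2.1%.

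**Dilution of the ratio.** Assume a hazard ratio of 2.0 up to 28 days after the last dose and 1.0 later, with no dropout.

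- 8-week washout: (2×105 + 28 + 2×105)/(133 + 105) = 448/238 = 1.88.
- 10-week washout: (2×105 + 42 + 2×105)/(147 + 105) = 462/252 = 1.83.

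**Dilution on the incidence scale.** Assume also a background risk of 10% per 4 weeks, so h = −ln(0.9)/28 = 0.00376 per day. The risk in a window is 1 − exp(−h × days), with tirzepatide days up to 28 days after the last dose counted twice. Each treatment's incidence is the mean of its two windows.

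| Rule | Tirzepatide | Placebo | Difference |
|---|---|---|---|
| SAP, 8-week washout | (59.2 + 54.6)/2 = 56.9% | (39.4 + 32.6)/2 = 36.0% | 20.9 points |
| SAP, 10-week washout | (61.3 + 54.6)/2 = 57.9% | (42.5 + 32.6)/2 = 37.6% | 20.4 points |
| Common 28-day tail | 54.6% | 32.6% | 22.0 points |

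The loss is 1.1-1.6 points, or 0.4-0.6 of a patient in 38.

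**Unequal dropout.** Assume 19 patients per sequence and all 8 dropouts on tirzepatide, each observed for 39 + 28 = 67 days. The figures are mean observed days per exposed patient.

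- Split 4+4 between periods, 8-week washout: tirzepatide (15×133 + 15×105 + 8×67)/38 = 108.1; placebo (19×133 + 15×105)/34 = 120.6; ratio 1.12.
- Split 4+4, 10-week washout: tirzepatide (15×147 + 15×105 + 8×67)/38 = 113.6; placebo (19×147 + 15×105)/34 = 128.5; ratio 1.13.
- Common 28-day tail: tirzepatide (30×105 + 8×67)/38 = 97.0; placebo 105; ratio 1.08.
- Extreme case, all 8 in Period 1 and every washout 10 weeks: tirzepatide (11×147 + 19×105 + 8×67)/38 = 109.2; placebo (19×147 + 11×105)/30 = 131.6; ratio 1.21.
- Opposite case, all 8 in Period 2 and 8-week washout: tirzepatide (19×133 + 11×105 + 8×67)/38 = 111.0; placebo (133 + 105)/2 = 119.0; ratio 1.07.

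**The case against.** The best defence is that TEAEs are tabulated by treatment, not by period. With 1:1 sequences each treatment gets the same mix of windows, so the inequality cancels between treatments when follow-up is complete. This stands, and it rules out several stronger readings that a reader might infer:

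- *That the rule produces a spurious difference.* The assumed background risk gives 39-43% in Period 1 windows and 33% in Period 2 windows with no drug effect. That compares periods, and the SAP specifies no TEAE table of that kind.
- *That 12-17% of the excess events are lost.* Under the model above, the expected excess is 210h per pair of windows with or without the late days. Only the ratio shrinks, and no TEAE rate ratio is planned.
- *That unequal dropout makes placebo time 12-21% longer because of this rule.* Most of the 4+4 gap (1.08) comes from dropout itself and remains under a common tail. The rule adds about 3-5 points. The upper end needs every dropout in one period of one sequence and every washout at its maximum. The documents give no dropout split by treatment, and dropout mainly on placebo would reverse the direction.

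The plan also has partial safeguards. TEAEs are split by relationship to study drug, listings cover the washout and show treatment and period, and safety statistics are descriptive. Washout data are recorded once, at the Period 2 first-dose visit; any under-reporting would reduce the dilution.

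It is also fair to say that nothing in the documents shows adverse event risk ending at 28 days, and that the SAP rule keeps late events in the treatment column. The proposed fix answers this by keeping those events visible. Listings and relatedness judgements do not by themselves restrict the overall incidence table to comparable windows.

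**Conclusion.** The point holds as a minor one. The rule has no cut-off and attaches tails of 56-70 and at most 28 days to the two periods, so 12-17% of each treatment's pooled window lies more than 28 days after the last dose. These figures follow from the documents. The effect sizes rest on assumptions: a hazard ratio of 2.0 ending at 28 days, a constant background risk of 10% per 4 weeks, and 8 dropouts all on tirzepatide at mid-period. Under them the ratio falls to 1.83-1.88, the risk difference falls by 1.1-1.6 points, and the observation-time ratio is 1.12-1.13 instead of 1.08 in the 4+4 case. None of this shows a systematic bias between treatments or a safety conclusion that would reverse.

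There is a related gap. A patient who stops in Period 1 has follow-up but no Period 2 treatment, so the follow-up rule read literally assigns those events to an arm never received.

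A reader might extend the point to hypoglycemia. SAP 6.10.5.2 states no washout attribution rule, and Protocol 10.3.1.2 plans those summaries by treatment group and visit as well as overall, so no error is claimed there.

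**What to change.** In SAP 6.10.2, count in the by-treatment TEAE tables only events with onset from the first dose of a period to 28 days after the last dose of that period, assigned to the treatment taken in that period. The 28 days is the protocol's own follow-up length and gives completers a window of 77 + 28 = 105 days in both periods. It also settles attribution for patients who stop in Period 1. Show washout events after day 28 in a separate row and listing labelled with the prior treatment. Use the same row for any later event in a discontinued patient, whose follow-up may run from the early termination visit.

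For consistency the same window may be used for the overall by-treatment hypoglycemia summary; this is optional.

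The cost is a change of SAP wording and one date condition in the adverse event programs, with no new data. The downside is that late events leave the main by-treatment count, though they stay visible in their own row.

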5.1.2. Treatment

The tirzepatide treatment period will consist of a step-wise dose escalation. The starting dose will be 2.5 mg QW for 2 weeks, followed by an increase to 5 mg QW for 2 weeks, and 10 mg QW for 4 weeks until the 15-mg dose is reached and maintained for the remainder of the treatment period (4 weeks), see Section 5.5 (Justification for Dose) for further details. Patients will visit the clinical research unit (CRU) as outpatients 1 week after administration of the first dose (Week 2) and for administration of the first of each escalated dose during both the tirzepatide and placebo treatment periods (Weeks 3, 5 and 9 of each treatment period). Study drug will be dispensed to the patient at these visits for self-administration on all other dosing days. Telephone visits will be conducted to ensure that outpatient dosing occurs and to monitor safety.

The schedule of clinic visits and study procedures during the treatment periods, including sampling for immunogenicity and pharmacokinetic (PK) assessments, are provided in Section 2 (Schedule of Activities).

Patients will attend the CRU as outpatients on Week 12 of each treatment period to receive the final dose of study drug. The following day, patients will be admitted to the CRU and will undergo a hypoglycemic clamp procedure as detailed in Appendix 6.

Patients who initiate rescue medication for treatment of severe hyperglycemia (Section 7.4.1.2 Management of Hyperglycemia) during the study may continue in the study but rescue medication will be discontinued 1 week before the clamp procedure to avoid interference with measurements planned during the hypoglycemic clamp.

Patients who permanently discontinue study treatment early, irrespective of the reason, will be discontinued from the study (Section 8.1 Discontinuation from Study Treatment). They will perform an early termination (ET) visit as soon as possible after the decision to discontinue study treatment, followed by a safety follow-up visit up to 4 weeks later.

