7.8. Treatment after the End of the Study

Not applicable. Tirzepatide will not be made available to patients after completion of the study.

8. Discontinuation Criteria

Patients discontinuing from the study prematurely for any reason should complete ET visit and safety follow-up visit procedures according to Section 2 (Schedule of Activities).

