6.1. Populations for Analyses

For the purpose of analysis, [Table GPHG.2](#) defines 3 analysis sets.

Table GPHG.2. Analysis Populations/Data Sets

Population/Data Set	Definition
All randomized population	All patients who are randomly assigned to a treatment sequence.
Safety population	All randomized patients who are exposed to at least 1 dose of study drug (tirzepatide or placebo), regardless of whether they completed all protocol requirements.
PD analysis set *	Evaluable PD data from all randomized patients who are exposed to at least 1 dose of study drug and complete both hypoglycemic clamp procedures.

Abbreviations: PD = pharmacodynamic.

* Protocol deviations will be considered for their severity/impact and taken into consideration whether subjects should be excluded from PD analysis set for hypoglycemic clamp data related analyses.

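### SAP 6.10.2 assigns all follow-up TEAEs to the Period 2 arm, which does not fit patients who enter follow-up without ever being dosed in Period 2

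*SAP*

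**What the plan says.** SAP 6.10.2 counts as treatment-emergent any event that first occurs, or worsens, after the first dose of Period 1. On presentation it says: "Treatment-emergent adverse events will be summarized by treatment, severity and relationship with study drug". Two sentences then deal with off-drug time. For the gap between periods: "For TEAEs in wash-out period, the treatment arm from Period 1 will be used for summary". For the time after treatment: "For TEAEs in follow-up period, the treatment arm from Period 2 will be used". No exception is stated for a patient who was never dosed in Period 2.

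Protocol 5.1.2 says: "Patients who permanently discontinue study treatment early, irrespective of the reason, will be discontinued from the study". These patients have an ET visit, "followed by a safety follow-up visit up to 4 weeks later". The opening of Protocol Section 8 extends this beyond patients who stop drug: "Patients discontinuing from the study prematurely for any reason should complete ET visit and safety follow-up visit procedures". The Follow-up / Early Termination table in Protocol Section 2 schedules AE collection at both visits and times the final follow-up as "Within 4 weeks from last dose/ET".

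SAP Table GPHG.2 puts every randomised patient with at least one dose into the safety population, "regardless of whether they completed all protocol requirements".

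**The concern.** The follow-up sentence works for a patient dosed in both periods, because the Period 2 treatment is then the last one taken. It does not work for a patient who leaves earlier. That patient is in the safety population, is followed for adverse events off drug, and has no Period 2 treatment.

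Adverse events are a secondary endpoint under an objective worded as a comparison of tirzepatide with placebo. The patients affected are early leavers, whose tolerability is of particular interest. If their follow-up events are entered under the other treatment, or under none, the by-treatment tables misstate tolerability for a group that may not be balanced between treatments.

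**Working it through.** **1. The plan's own figure.** Protocol 10.1 and SAP 5.2 give 30 completers and a 20% discontinuation rate. 30 / (1 − 0.20) = 37.5, rounded up to 38, which matches the plan. The allowance is 38 − 30 = 8 non-completers.

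**2. The rule applied to a patient never dosed in Period 2.** Randomisation is to a sequence (SAP 5.1), so each patient has a planned Period 2 arm from Day 1, whether or not it is taken. The SAP does not say whether the Period 2 arm means planned or taken.

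| Patient | If planned arm | If treatment taken |
|---|---|---|
| Tirzepatide-first, never dosed in Period 2 | follow-up event goes to placebo, never given | no arm, so no column |
| Placebo-first, never dosed in Period 2 | follow-up event goes to tirzepatide, never given | no arm, so no column |
| Dosed in Period 2 | correct | correct |

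Neither reading gives the right column in the first two rows.

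**3. Whether other text repairs this.** SAP 6.6.2 adjusts compliance for early termination, but 6.10.2 has no matching provision. SAP Section 8 clarifies the analysis populations and says nothing on attribution.

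**4. How many patients.** The documents do not split the 8 by period or sequence. The share leaving before Period 2 dosing is therefore an assumption, shown over its full range. I also assume 19 patients per sequence, all dosed, and a denominator of patients exposed to each treatment (the SAP does not state the denominator). Let k be the number leaving before Period 2. If they are spread evenly over the sequences, each treatment has 19 + (19 − k/2) = 38 − k/2 exposed patients. If all k come from one sequence, that sequence's first treatment has 38 exposed and the other has 38 − k.

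| Share before Period 2 | k | k/38 | Exposed per treatment, even split | Exposed, all from one sequence |
|---|---|---|---|---|
| 0% | 0 | 0% | 38 and 38 | 38 and 38 |
| 25% | 2 | 5.3% | 37 and 37 | 38 and 36 |
| 50% | 4 | 10.5% | 36 and 36 | 38 and 34 |
| 75% | 6 | 15.8% | 35 and 35 | 38 and 32 |
| 100% | 8 | 21.1% | 34 and 34 | 38 and 30 |

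**5. Effect of one patient on a column.** 1/38 = 2.6, 1/36 = 2.8 and 1/34 = 2.9 percentage points. Only if more than 4 leave before Period 2, mostly from one sequence, does a column fall below 34. The extreme is 1/30 = 3.3 points. These are ceilings per patient with a new follow-up event. The column that should hold the event loses a patient only if that patient did not already have the same event there.

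**6. Whether drug is still present.** With the stated half-life of about 5 days, the fraction remaining t days after the last dose is 0.5^(t/5): 38% at 7 days, 14% at 14 days and 2% at 28 days. An early follow-up event in a tirzepatide-first leaver can therefore occur with tirzepatide still in the body.

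**The case against.** The best reply is that this is an ambiguity rather than a wrong assignment. If the Period 2 arm means treatment taken, the rule is silent for these patients. Nor is follow-up defined for early terminators: the final follow-up is listed as Visit 17, Week 36, and a programmer might class off-drug time after Period 1 as washout, which goes correctly to the Period 1 arm. For a patient who withdraws during the washout, events before withdrawal are placed correctly in any case.

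This stands in part. A reader might infer that every such event will be tabulated under a treatment never received. The documents do not support that, because it holds only under the planned-sequence reading. The other reading still leaves the event without a column. The washout route is not in the text either: Protocol 5.1.3 defines the washout as the interval between the final Period 1 dose and the first Period 2 dose, and these patients have no Period 2 dose.

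A reader might also infer that the rule makes tirzepatide look better tolerated. Protocol 3.2 describes dose-related gastrointestinal events, and drug-related vomiting is a listed reason for permanent discontinuation in Protocol 8.1.1, so more leavers on tirzepatide is plausible. But the documents give neither the split of discontinuations by treatment nor a follow-up event rate. Placebo-first leavers push the error the other way under the planned-sequence reading. The intolerance that causes a stop normally begins on treatment and is counted there. The direction is not established.

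Finally, the harm is contained. The AE analysis is descriptive, SAP 6.10 listings show treatment and period, and that section promises an AE summary only for events in at least 10 patients. Listings let a reader trace individual cases, but they do not correct a by-treatment table.

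**Conclusion.** The rule as written is faulty for an identifiable group: patients in the safety population who enter follow-up without having been dosed in Period 2. Their new-onset follow-up events would be misplaced in, or lost from, the by-treatment TEAE summaries, depending on how the arm is read.

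The size is modest and uncertain. Between 0 and 8 of 38 patients could be affected. At 4, spread evenly by sequence, 36 patients are exposed to each treatment and one patient is worth up to 2.8 percentage points. Over 34 to 38 exposed, the range is 2.6 to 2.9. This rests on the planned dropout allowance, equal sequence sizes and exposed-patient denominators.

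The net effect would favour tirzepatide only if more of the early leavers are tirzepatide-first, which the documents do not tell us. The primary glucagon analysis is unaffected, since it uses patients who complete both clamps. The point merits correction because the error is in a stated rule and is nearly free to remove.

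**What to change.** Replace the follow-up sentence in SAP 6.10.2 with:

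*TEAEs in the follow-up period are assigned to the last study treatment actually received before onset (the Period 1 treatment for patients never dosed in Period 2). For patients who terminate early, follow-up starts at the ET visit or the discontinuation decision, whichever is earlier.*

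State also that the denominator for each treatment is the number of patients who received at least one dose of it, so that no event enters a numerator without its patient in the denominator.

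With this wording the number of patients whose follow-up events are misattributed is 0, whatever the split of discontinuations. The cost is a short SAP edit and one programming condition on dose dates already recorded. No new data are needed.
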